8.1.3.3 Participant Loss to Follow-Up

Participants that do not return for scheduled appointments without notice may be deemed lost-to follow-up (LTFU). Up to three attempts will be made to contact enrolled participants who miss a follow-up interval on phone and/or email, at each interval missed. Participants will be recorded as LTFU if they are absent and uncontactable for two consecutive assessments. Singular attempts to contact LTFU participants at long-term assessment intervals may still be attempted. If a participant previously marked as LTFU makes contact or returns for clinical review, they will be asked if they would like to withdraw from or continue active participation in research.

8.2 RANDOMISATION

Block randomisation will be performed to achieve balance in the allocation of participants to the different treatment arms throughout the course of the recruitment period. Fifteen blocks will be generated, with three multiples of each treatment arm per block. As a result, for every 12 randomly assigned treatment allocations, each intervention arm will have a comparable number of participants.

The randomisation sequence will be concealed in sequentially numbered sealed, opaque envelopes. The randomisation procedure will be administered by a research assistant who will not be blind to allocation for the duration of the study. They will open an envelope and reveal the allocation to the patient. As all treatment groups involve a hand therapy session, all participants will be provided with a referral for hand therapy by their referring surgeon when enrolled in the study. A dual randomisation procedure will be implemented, with one envelope opened at baseline and the other at the 6 week interval. At the baseline appointment, the assessor will open an envelope to reveal whether the participant will be receiving a splint.

A second randomisation will occur at 6 weeks to reveal whether the participant is to have a cortisone injection. Each envelope will contain a sheet of paper with the intervention group, as listed below.

Group A Hand Therapy (HT)	Group B HT + Splint	Group C HT + Cortisone	Group D HT + Splint + Cortisone
-------------------------------------	-------------------------------	----------------------------------	---

If randomly allocated into Group C or Group D, the participant's study surgeon will issue a referral for a cortisone injection to be administered at Brisbane Private Imaging, 6 weeks after the baseline appointment. The treating surgeon will not be blind to allocation to maintain standard medical care.

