8.1.1.1 Orthopaedic Surgeon Referral

Surgeons involved in the study will identify eligible study participants at the time of presentation to clinical appointments, based on the inclusion and exclusion criteria (*Eligibility Criteria, 6.1*). Patients with injuries deemed suitable for randomised conservative management by the treating surgeon, will be informed of the study. If the participant is interested in participation or would like more information, they will be referred to the Brisbane Hand & Upper Limb Research Institute. At the time of referral to the Brisbane Hand & Upper Limb Research Institute, the surgeon will complete a research referral indicating the participant's eligibility for study participation (Appendix 14.1). A research assistant will explain in detail the procedures, risks and benefits associated with the study and provide the Participant Information and Consent Form (PICF) for the participant to consider.

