8.1.2 Consent and Enrolment

Patients will be screened for eligibility and suitability by the referring surgeon. Consent procedures will be carried out by research assistants in line with the NHMRC National Statement on Ethical Conduct in Human Research (2007). After review of the Participant Information Consent Form (PICF) and acknowledging that they have understood the proposed research and the implications of participation, patients who voluntarily elect to participate will be asked to sign the consent form (Appendix 14.2). Once a participant has consented and completed their pre-treatment assessment, they will be randomised and allocated to an intervention group.

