9 DATA MANAGEMENT AND ANALYSIS

9.1 SAMPLE SIZE

180 participants will be recruited in the study, with 45 in each of the four groups. Sample size calculations were performed to detect an effect size suitable for the primary outcomes of pain and function, using the Patient Rated Wrist and Hand Evaluation (PRWHE).

The minimal clinically important difference (MCID) for pain and function in patients with wrist injury using the PRWHE is 14 points with a standard deviation of (Sorensen, Howard, Tan, Ketchersid, & Calfee, 2013). Using a global rating of change as an anchor, a minimum change of 5 points out of 15 is required for patients to reliably detect a notable improvement in symptoms and function at 3 months post intervention. To ascertain a clinically significant change in pain and function perceivable by the patient, the project has been designed to detect a relatively large effect size. It is not necessary to detect small effects in patient outcome scores, as clinically this small change is not perceivable by patients. Effect size (f) was set at 0.29, to allow detection of a medium-large effect.

The statistical test used to analyse outcomes data will be a factorial ANOVA, to analyse fixed effects, special, main effects and interactions. This will allow a comparison of treatment groups

compared to the control (Group A) and also examine the interactions between combination interventions (Group D).

- Effect size (f) = 0.29
- Type-I error (α) rate = 0.05
- Power (1- β err prob) = 80% (0.8)
- Number of groups (n) = 4
- Numerator df ($n - 1$) = 3

The above parameters are entered into sample size calculation software *G*Power* (Version 3.1.9.4), with the result that the study must recruit a minimum of 134 participants to achieve 80% power.

F tests - ANOVA: Fixed effects, special, main effects and interactions

Analysis: A priori: Compute required sample size

Input:	Effect size f	=	0.29
	α err prob	=	0.05
	Power (1- β err prob)	=	0.80
	Numerator df	=	3
	Number of groups	=	4
Output:	Noncentrality parameter λ	=	11.2694000
	Critical F	=	2.6742856
	Denominator df	=	130
	Total sample size	=	134
	Actual power	=	0.8013103

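### The fixed, disclosed block size of 12 lets anyone holding the full tally, for certain only the randomising assistant, partly predict the splint allocation at enrolment

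*Protocol*

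**What the plan says.** Protocol section 8.2 sets the allocation scheme: "Fifteen blocks will be generated, with three multiples of each treatment arm per block". It gives the block length again by noting that "for every 12 randomly assigned treatment allocations, each intervention arm will have a comparable number of participants". Section 9.1 gives the total: "180 participants will be recruited in the study, with 45 in each of the four groups".

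On concealment, section 8.2 says: "The randomisation sequence will be concealed in sequentially numbered sealed, opaque envelopes". On who knows what, it says: "The randomisation procedure will be administered by a research assistant who will not be blind to allocation for the duration of the study", and of the surgeon: "The treating surgeon will not be blind to allocation to maintain standard medical care". The patient is told the allocation too.

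On entry to the trial, section 8.1.1.1 says: "Patients with injuries deemed suitable for randomised conservative management by the treating surgeon, will be informed of the study". Section 8.1.2 adds: "Consent procedures will be carried out by research assistants". Section 5.2 names one site.

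Section 8.2 also describes two openings, one at baseline for the splint and one at 6 weeks for the injection. It then says that each envelope holds a sheet with the intervention group and lists the four groups. These two statements do not agree on what the baseline envelope shows.

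Consent and baseline assessment must come before the envelope is opened (sections 5.1, 8.1.2 and 8.3.3). Section 8.2 mentions no variation in block size, no off-site allocation and no withholding of the block size from those who recruit.

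**The concern.** Concealment requires that nobody who influences entry can tell what comes next. Sealed envelopes meet that only if the next slip cannot be deduced from earlier ones. With a known, constant block and visible past allocations, a simple count shows which allocations remain. Late places in a block may be known outright, and earlier ones can be guessed better than by chance.

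The decisions open to influence come before consent: whether a surgeon regards a patient as suitable, when the appointment falls, and how the trial is presented. If these depend on the expected allocation, the splint and no-splint groups can differ at entry. The primary outcome, PRWHE, is reported by patients who know their treatment. The blinded collection of clinical outcomes listed in section 4.2 acts after enrolment and does not protect against this. Adjusting for baseline PRWHE or occupation deals with imbalance in those measures, but not with unrecorded impressions of prognosis or motivation.

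**Working it through.** **Inputs.** Fifteen blocks with three places per arm and four arms (8.2); 180 participants, 45 per arm (9.1); splint arms B and D, no-splint arms A and C (5.1); recruitment over 24 months (5.3); injection opened at 6 weeks (8.2).

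**The plan's own figures.** 4 × 3 = 12 per block; 15 × 12 = 180; 15 × 3 = 45 per arm. These agree, and they leave no room for any block to differ from 12.

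**Splint allocation, full tally known.** Each block holds 6 splint and 6 no-splint places. The observer always guesses whichever has more places left.
- Expected correct guesses per block: 6 + 2^11 / C(12,6) − 0.5 = 6 + 2048/924 − 0.5 = 7.72. Then 7.72/12 = 64%, against 50% by chance.
- Expected places known with certainty, that is, the run at the end of a block when only one kind remains: the sum over k = 1 to 6 of 2 × C(12−k, 6) / C(12,6) = 2 × (462 + 210 + 84 + 28 + 7 + 1)/924 = 1584/924 = 1.71 of 12, or 14.3%. Over 15 blocks, 1.71 × 15 = 25.7, about 26 of 180.

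**Whole group, full tally known.** This applies only if the baseline envelope shows the full arm.
- Certain places per block: 4 × [3/12 + (3×2)/(12×11) + (3×2×1)/(12×11×10)] = 4 × 0.30 = 1.2, or 10.0%; 1.2 × 15 = 18 of 180.
- Best guess, by simulation of 20,000 blocks: right 44% of the time, against 25% by chance.

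**Timing under the two-stage procedure.** 180/24 = 7.5 participants per month, so a block fills in 12/7.5 = 1.6 months, about 7 weeks. The injection status of a participant is opened 6 weeks after baseline. When most members of a block enrol, the injection status of nearly all earlier members is therefore still sealed. When a participant's own status is opened, that participant is already in the trial.

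**Partial tally.** The protocol does not give the number of surgeons, so a range is assumed. Suppose surgeons share recruitment equally, each sees only their own patients' splint allocations, and each knows where blocks begin and end. By simulation, with 2 surgeons the best guess is right 56% of the time and fewer than 1 of 180 allocations is certain. With 4 surgeons it is right 54% of the time and essentially none is certain.

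**Effect of varying the block size.** The simulation drew sizes of 8, 12 or 16 at random with equal probability. The observer had the full tally and knew the set of sizes, but not the current one.
- Certain splint allocations: 14.3% falls to about 1.6%.
- Best guess for the splint: stays near 64%.

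A list with exactly five blocks of each size would leave an observer who also knew that composition somewhat more certain towards the end, but still far below 14.3%.

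**The case against.** A fixed block of three times the number of arms in numbered opaque envelopes is a conventional choice, and nothing in section 8.2 is arithmetically wrong. Four further arguments count against a stronger claim.

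- A reader might infer that everyone who recruits sees the whole sequence. The protocol does not say so. It unblinds the treating surgeon, but does not say that one surgeon sees a colleague's allocations. It refers to research assistants in the plural for consent and to one assistant for randomisation, without saying that they are the same person. This stands: the 64% and the 26 of 180 are upper bounds.
- A reader might take the four-arm figures as the exposure at enrolment. Under the two-stage procedure they largely cannot be used to steer entry, for the timing reason shown. This also stands. They matter only if the baseline envelope shows the whole group, on which section 8.2 is inconsistent.
- A reader might infer that selection bias will occur, or that its size is known. A guess rate is not a bias in PRWHE points, and the documents give no basis for converting one into the other. Severity and occupation are recorded before allocation, so imbalance in them can be seen and adjusted for.
- Varying the block size barely changes the average guess rate for someone who knows the possible sizes. This is correct, so the sizes must also be withheld.

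The weakness itself remains: the block length is constant and disclosed, an unblinded assistant sees every opening, and unblinded surgeons have discretion over entry. Requiring consent and baseline assessment before opening does not remove it, because steering would happen earlier.

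**Conclusion.** The point holds as a partial weakness of concealment, chiefly for the splint comparison. With the full tally, which only the randomising assistant is sure to hold, the splint allocation can be guessed correctly 64% of the time against 50%, and about 26 of 180 (14.3%) are certain. A surgeon with only their own patients' allocations would do less well: 56% to 54% for 2 to 4 surgeons under the stated assumptions. The cortisone comparison is largely protected if the two-stage opening is followed. If the baseline envelope shows the whole group, the upper bounds are 44% against 25%, with about 18 of 180 certain.

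These figures assume that the observer knows the block size, counts accurately and guesses optimally. They measure opportunity, not whether anyone would use it. The documents do not support saying that all allocations can be predicted or that enrolment will be steered. The sample size calculation is unaffected.

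**What to change.** In section 8.2:

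- Replace the fifteen blocks of 12 with randomly ordered permuted blocks of varying size. Five each of 8, 12 and 16 would do: 5 × (8 + 12 + 16) = 180, and 5 × (2 + 3 + 4) = 45 per arm.
- Have the list and envelopes prepared by someone who does not recruit, take consent or randomise.
- Keep the sizes in a restricted document that surgeons and research assistants do not see, and say in the protocol only that sizes vary. This step is needed because variation alone removes most of the certainty but little of the better-than-chance guessing.
- State whether the baseline envelope shows splint status only or the whole group, so that the two descriptions agree.

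No new rule on the order of consent, baseline assessment and opening is needed, since the protocol already has one.

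The cost is generating a new list and refilling the envelopes. The one statistical downside is a small imbalance between arms if recruitment stops inside a block. The total and the numbers per arm do not change.

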Using historical participant retention at the Brisbane Hand and Upper Limb Clinic as a model, an attrition rate of 25% is anticipated. If 134 is the smallest remaining cohort after attrition (75% retention) required to achieve 80% power, the minimum recruitment sample required would be 179. Due to the balanced study design necessitating even group numbers, the target recruitment sample size is 180 participants, with 45 participants allocated to each group.

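### Section 8.2 leaves open whether Group A–D is fixed at baseline or completed by a second randomisation at week 6, and no rule covers a participant whose second envelope stays unopened

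*Protocol*

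**What the plan says.** Section 8.2 contains two descriptions of the allocation.

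- **Two-stage.** "A dual randomisation procedure will be implemented, with one envelope opened at baseline and the other at the 6 week interval". For the first envelope: "At the baseline appointment, the assessor will open an envelope to reveal whether the participant will be receiving a splint". For the second: "A second randomisation will occur at 6 weeks to reveal whether the participant is to have a cortisone injection".
- **Single four-arm list.** "Fifteen blocks will be generated, with three multiples of each treatment arm per block". On the envelope contents: "Each envelope will contain a sheet of paper with the intervention group, as listed below"; the list that follows is the four groups A to D.

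Other sections place the allocation at baseline. Section 8.1.2: "Once a participant has consented and completed their pre-treatment assessment, they will be randomised and allocated to an intervention group". Section 5.1 says the same in substance. Section 8.4 treats the allocation as complete at the baseline appointment and has radiology appointments arranged from then if needed. Section 9.1 sets the target: "the target recruitment sample size is 180 participants, with 45 participants allocated to each group".

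On missed visits, Section 8.1.3.3 states: "Participants will be recorded as LTFU if they are absent and uncontactable for two consecutive assessments". No section says how a participant is classified if the week-6 envelope is never opened.

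**The concern.** Who is randomised, to what and when is protocol content. An analysis plan can define analysis sets, but it cannot supply an allocation that was never made.

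The splint factor starts at baseline, and Section 8.4.2 prescribes six weeks of full-time wear. Attendance at week 6 therefore comes after the splint has had time to influence it. If the cortisone allocation is made only at that visit, having a complete A–D label depends on something that happens after the splint randomisation. Restricting the splint contrast to people with a complete label loses the protection of the baseline randomisation. Labelling the others as no-injection puts poor attenders on one side of the cortisone contrast only. The primary objective asks about splint and cortisone, alone and combined, so both contrasts matter.

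**Working it through.** **1. The plan's own figures.** Section 9.1 gives f = 0.29, alpha = 0.05, power 80%, four groups and numerator df 3.
- Noncentrality: 134 × 0.29² = 11.2694. With denominator df 130 and critical F 2.6743, power is 0.8013. All match the protocol.
- Attrition of 25%: 134 / 0.75 = 178.7, so 179, rounded to 180.
- Blocks: 15 × 12 = 180, and 15 × 3 = 45 per arm.
- After 25% loss: 180 × 0.75 = 135, power 0.805.

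The sample size is sound. The defect lies in group assignment.

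**2. Can the statements in Section 8.2 be carried out together?**
- If the baseline envelope holds the A–D group, opening it discloses cortisone status at once, and nothing is left to reveal at week 6.
- If the baseline envelope shows splint status only, it does not hold the A–D group.
- If week 6 is a fresh randomisation, a second list is needed. Only one is described, and its 45 per arm would not be guaranteed for groups completed later.

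They cannot all hold.

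**3. Who is affected.** A participant who misses week 6 alone does not meet the two-consecutive-assessments rule, so stays enrolled and can give a 12-week PRWHE (Section 8.5.1 window: 2 to 4 months). A factorial ANOVA with four groups needs a level of both factors for each record. This record has one.

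**4. Scale.** Loss before week 6 is not given, so any size is conditional on assumptions. Suppose a share d of the 180 never has the second envelope opened. The number per arm with a complete label is 180(1 − d)/4. If those 180d people were counted as no-injection, they would form 180d / [180(1 − d)/2 + 180d] of that side.
- d = 5%: 9 people; 42.8 per arm; 9/94.5 = 9.5%.
- d = 10%: 18 people; 40.5 per arm; 18/99 = 18.2%.
- d = 25% (all stated attrition, as a ceiling): 45 people; 33.8 per arm; 45/112.5 = 40%.

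Only those who return at 12 weeks can affect the 12-week means. Assume 5% to 15% miss week 6 (9 to 27) and half return, so m = 4 to 13, rounded down, among the 135 measured.
- Excluding them removes 4/135 = 3.0% to 13/135 = 9.6% of measured outcomes from the splint contrast.
- Counting them as no-injection, if they differ from the rest by D points, moves that side's mean by D × m / [(135 + m)/2]. With D = 14, borrowed from the protocol's minimum relevant PRWHE change only as a yardstick: 14 × 4/69.5 = 0.8 and 14 × 13/74 = 2.5 points.

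The shift is proportional to D and vanishes at D = 0. This shows scale and is not an estimate.

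**The case against.** The strongest reply is that the group is in fact fixed at baseline. The blocked four-arm list is generated in advance, the envelopes are numbered, and the week-6 step is said to reveal cortisone status. On that reading disclosure is staged, and an early leaver's group can be read from the list. This stands as a possible reading. It does not remove the point: the text also calls week 6 a second randomisation, an envelope holding A–D would defeat the staging, and nothing tells staff to recover an unopened allocation.

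Three further replies carry weight.
- Most people who leave before week 6 will have no 12-week score under any scheme and fall within the 25% allowance. The problem specific to this design is the smaller set who miss week 6 and return.
- Section 8.5.1 allows ±10 days at week 6, Section 8.1.3.3 allows up to three contact attempts per missed interval, and nothing says the envelope lapses after a missed appointment. That shrinks the set but does not empty it.
- Splint status is known from baseline, so an analysis could keep these people in the splint contrast. It could, but the four-group ANOVA as described does not do so by itself.

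A reader might infer that such participants belong to no group, or that the plan drops them or counts them as controls. The first holds only if week 6 is a true randomisation. The second is a possible consequence that the protocol nowhere states. Nor does Section 8.1.3.2 promise attrition by group: it promises the attrition rate, and wrist outcomes of those treated outside the protocol.

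**Conclusion.** The contradiction is established from the text: Section 8.2 conflicts with itself and with Sections 5.1, 8.1.2 and 8.4 on when A–D is determined. The analytic consequence is conditional. It arises if week 6 is a true second randomisation and some participants miss that visit but are measured at 12 weeks. Then the planned analysis must exclude them from the splint contrast or give them a cortisone level that was not randomised.

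The size is unknown; the ranges above rest wholly on assumed rates and an assumed difference. A reader might also infer that the trial is underpowered or that 45 per group is miscalculated. Neither follows: the arithmetic reproduces, and 45 per group is a recruitment target with no timing attached. The change is worth making because it is cheap and because allocations are hard to repair once they have accrued.

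**What to change.** Reconcile Sections 5.1, 8.1.2, 8.2, 8.4 and 9.1 by choosing one procedure.

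- **(a) Group fixed at baseline.** State that A–D comes from the single four-arm list and is disclosed in two steps by two separately numbered envelopes, the first showing splint status only and the second cortisone status only. Analyse every participant in the listed group, even if the second envelope is never opened.
- **(b) Two randomisations.** Describe the second list. Estimate the splint effect from everyone randomised at baseline, and the cortisone effect from everyone randomised at week 6, injected or not. Never count a participant without a second allocation as no-injection by default. State that four-group comparisons apply only to those randomised at week 6. D versus C and D versus A include the splint and so keep selection on week-6 attendance; D versus B differs only in cortisone and does not have this problem.

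Either option costs protocol wording and a participant flow chart, with no extra participants or visits. Under (b) the two factors have slightly different denominators, and the groups may not be exactly 45 each.

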5.1 INTERVENTION GROUPS

This study will have an active control group (Group A) and three intervention groups;

Group A: will receive hand therapy

Group B: will receive a thermoplastic wrist splint + hand therapy

Group C: will receive a corticosteroid injection to the TFCC + hand therapy

Group D: will receive a thermoplastic wrist splint + corticosteroid injection to the TFCC + hand therapy

Participants will be randomly allocated to a treatment group following informed consent and a baseline research assessment.

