8.4 TREATMENT INTERVENTIONS

Following the completion of all research data collection and randomisation allocation at the baseline appointment, the participant will have treatment appointments made with the hand therapist and radiologist if necessary.

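### Section 8.2 stages the splint and injection allocations six weeks apart, but its envelopes hold the full group A–D, so the first one opened gives away the injection

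*Protocol*

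**What the plan says.** Section 8.2 describes two steps: "A dual randomisation procedure will be implemented, with one envelope opened at baseline and the other at the 6 week interval". It gives each step its own content. For the first, "At the baseline appointment, the assessor will open an envelope to reveal whether the participant will be receiving a splint". For the second, "A second randomisation will occur at 6 weeks to reveal whether the participant is to have a cortisone injection".

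The next sentence gives the envelopes a different content: "Each envelope will contain a sheet of paper with the intervention group, as listed below". The list that follows is the four complete groups: A (hand therapy), B (with splint), C (with cortisone) and D (with both).

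The allocation list is also built on complete groups: "Fifteen blocks will be generated, with three multiples of each treatment arm per block", so that "for every 12 randomly assigned treatment allocations, each intervention arm will have a comparable number of participants". No separate list is described for the week-6 step. The research assistant who administers the procedure is unblinded throughout and tells the patient the result.

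Section 8.4 says that, once data collection and allocation at the baseline appointment are finished, "the participant will have treatment appointments made with the hand therapist and radiologist if necessary". Section 8.1.2 describes a single allocation to a group after the pre-treatment assessment. Section 5.1 says: "Participants will be randomly allocated to a treatment group following informed consent and a baseline research assessment".

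**The concern.** A sheet naming A, B, C or D cannot show splint status without also showing injection status. If it is opened at baseline, the week-6 step has nothing left to decide.

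The injection is given at 6 weeks (8.2, 8.4.3) and the primary endpoint is at 12 weeks (8.5.1). Until week 6, A and C are treated alike, and so are B and D. Treatment is not blinded and the PRWHE is patient-reported. A participant who knows an injection is coming, or is not, may report differently, seek other treatment or leave. The protocol supplies the routes: 8.1.3.1 lets a consented participant withdraw rather than follow the allocation, and 8.1.3.2 ends active participation once outside treatment is taken. Differences that arise this way before any injection would enter the week-12 comparison, and analysis could not cleanly remove them.

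Staff could also follow different sentences of 8.2 for different participants, leaving some informed early and others not.

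**Working it through.** **1. The plan's own figures.** 15 blocks × (3 × 4 arms) = 180, and 15 × 3 = 45 per arm, as in 9.1. They reproduce as one randomisation to four complete arms.

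**2. The passages side by side.**

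| Place | Known at baseline | Left for week 6 |
|---|---|---|
| 8.2, two-step description | splint only | injection |
| 8.2, envelope content | full group, so both | nothing |
| 8.2, block list | complete arms, one list | no second list described |
| 8.1.2 | allocation to a group | nothing mentioned |
| 8.4 | whether a radiologist is needed | nothing |
| 5.1 | order only: consent, assessment, allocation | compatible with either |

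The qualifier in 8.4 does not remove the conflict. Whether a radiologist is needed can be judged at baseline only if injection status is known then.

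**3. What a group label discloses.** A = neither, B = splint, C = injection, D = both. Given the label, the probability of injection is 0 or 1. Given splint status alone it is 45/90 = 0.5. Only the second leaves something to reveal at week 6.

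**4. Could the second envelope be a fresh A–D draw?** Two of the four labels would disagree with the first envelope on splint: 2/4 = 0.5, or about 90 of 180 participants. Simulating pairs of such lists (5,000 runs) gives 0.4997. This reading does not work either.

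**5. Exposure.** If the A–D sheet is opened at baseline, injection status is known for 6/12 = half of the primary period.

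**6. Can the list be kept?** Yes. If each line is split into a splint part and an injection part under one participant number, the arms remain 45 each. Two independent yes/no lists would not guarantee this: simulation (20,000 runs) gives a mean cell size of 45, SD about 3.5 and a 95% range of 38 to 52. The sample size is untouched: λ = 134 × 0.29² = 11.2694, critical F = 2.6743, power = 0.8013; 134/0.75 = 178.7, rounded up to 179, then 180.

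**7. Secondary: predictability with fixed blocks of 12.** Assume someone who knows the block size and every past allocation and always guesses the most frequent remaining option.

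- Splint yes/no (6:6, n = 6): expected correct guesses = n + 2^(2n−1)/C(2n,n) − ½ = 6 + 2048/924 − 0.5 = 7.72 of 12, or 64.3% (chance 50%). Certain in advance: 2n/(n+1) = 12/7 = 1.71 per block, × 15 ≈ 26 of 180.
- Four arms (3:3:3:3): recursion over remaining counts, E = max/total + Σ(countᵢ/total)·E(one fewer of i), gives 5.29 of 12, or 44.1% (chance 25%). Certain in advance: 1 + 2/11 + (2/11)(1/10) = 1.20 per block, × 15 = 18 of 180.

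**The case against.** The best defence is that 8.2 states the staged intent clearly, splint first and injection at 6 weeks, and that the sentence about the sheet may be loose or leftover wording. That is possible. The text cannot show which procedure operates, so early disclosure to all 180 participants is the consequence of following the envelope sentence, not an established fact. The contradiction remains, and 8.4 and 8.1.2 lean towards full allocation at baseline.

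It can also be said that the trial is open in any case: patients are told their allocation and expectation can act from week 6 to week 12 under either procedure. That stands. Early disclosure lengthens the exposure and moves it ahead of the treatment; it does not create it.

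A reader might infer more than the document supports:

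- *That a single four-arm list cannot serve two steps.* It can, as staged disclosure of one randomisation. What fails is the envelope content and the label of a second randomisation.
- *That the week-6 PRWHE is spoiled as a pre-randomisation measure.* The protocol never uses it so; 8.5.1 treats week 6 as an interim outcome assessment.
- *That 5.1 places full disclosure at baseline.* It gives only the order of events and does not mention radiology.
- *That a countable number of participants leave before their second envelope.* Section 9.1 gives 25% attrition without timing, so no figure follows. Participants leaving with injection undetermined also presupposes staged disclosure, which is incompatible with everyone knowing at baseline.

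Block predictability is a separate matter. It assumes perfect tracking, and the surgeon judges eligibility before referral, although research assistants still take consent.

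**Conclusion.** The contradiction within 8.2, and between its two-step description and 8.4 and 8.1.2, is real. On the envelope wording, injection allocation is disclosed six weeks early, covering half of the primary period, and the week-6 randomisation is empty. The size of any resulting bias in PRWHE cannot be calculated from the protocol. The conclusion rests on taking the envelope sentence literally; if staff already use component envelopes, the defect is one of documentation and the same amendment settles it. The block list, the 45 per arm and the sample size are sound. The fixed, printed block size is a lesser weakness: at most 64% correct guessing for splint, or 44% for four arms, under perfect tracking.

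**What to change.** - Keep the list of 15 blocks × 12. Split each line into two sealed, opaque envelopes bearing the same participant number. One reads only 'Splint' or 'No splint' and is opened at baseline. The other reads only 'Injection' or 'No injection' and is opened at 6 weeks, after the week-6 questionnaire is completed.
- Delete the A–D sheet from 8.2.
- Make the radiology booking in 8.4 follow the second envelope.
- Reconcile 5.1, 8.1.2, 8.2 and 8.4, and call the process staged disclosure of one randomisation.
- Secondarily, vary the block sizes and keep them from recruiting staff.

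**Cost:** reprinted envelopes, a short amendment, and less notice for radiology appointments. The sample size is unchanged. With varied block sizes, arm totals may differ slightly from 45.
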